- all modifications have been communicated to sites, and approved (including approval by the site's IRB of record) before the modification is implemented.
- all engaged participating sites will safeguard data as required by local information security policies.
- all local site investigators conduct the study appropriately.
- all non-compliance with the study protocol or applicable requirements will be reported in accordance with local policy.

The involvement of sites other than the MPRC (community day centers) will consist of an MPRC investigator (usually clinical research assistant) visiting the site with a laptop and testing material and taking the participant to a separate room for the training (and sometimes testing) intervention. If the local site has nursing or other medical staff who are willing to administer a lozenge that may contain nicotine, they may give the lozenge to the participant twice/week (usually Mon and Thur) prior to the cognitive training. Doctor's Orders will be provided for this by an MPRC physician on the protocol (Drs. [name], [name], or [name]). Beyond this, there is no involvement of local site investigators/staff beyond facilitating the work of the MPRC investigator visiting daily. The MPRC investigator will coordinate the time of their daily visits with the availability of the participant and day room. Local site investigators/staff may assist with this.

Despite this limited involvement, local site investigators/staff will be in possession of the most current version of the IRB protocol and consent document. The PI will also meet with local site staff and explain the study and associated procedures in person. All site staff will have the PI's contact information and vice versa.

If the site has an IRB (such as community day centers associated with the Sheppard Pratt Healthcare System), separate IRB approval will be obtained. All protocol modifications will also be submitted to the local IRB prior to implementation at that site. All changes relevant to this site will also be communicated to the local site investigators/staff.

No data will be stored at any of the non-MPRC sites.

All non-compliance with the study protocol or applicable requirements will be reported in accordance with local policy, irrespective of at which site it occurred.

2.2 *Describe the method for communicating to engaged participating sites including:

- reportable new information.
- problems.
- interim results.
- the closure of a study.

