- 2 * Discuss the research design including but not limited to such issues as: probability of group assignment, potential for subject to be randomized to placebo group, use of control subjects, etc.:

Volunteers with a DSM-IV diagnosis of schizophrenia or schizoaffective disorder will be recruited, screened, and allocated in a double-blind manner to either the Nicotine Group or the Placebo Group. All participants will be asked to perform 10 weeks of cognitive remediation training (Posit Science, Duncan, SC), with daily training sessions Monday through Friday. On Mondays and Thursdays, all participants receive a lozenge 20 min prior to the training. In the Nicotine Group, the lozenge will contain 2 or 4 mg of nicotine, depending on smoking status. In the Placebo Group, the lozenge will be a matched placebo.

Outcome measures (OCMs) are assessed on Wednesdays in week 0 (day before training starts), weeks 4, 7 and 10 (after the training session), and week 14 (four weeks after training ends). OCMs are assessed on a non-drug day (Wed) because we are not studying the acute effects of nicotine but nicotine-induced enhancement of longer-term training effects.

- 3 * Describe the relevant prior experience and gaps in current knowledge. Describe any relevant preliminary data:

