Volunteers who provide Informed Consent will be screened for all Inclusion/Exclusion criteria. SCREENING will include: - Verification of age. - The SCID, to determine the presence/absence of current psychiatric conditions. For most patients, a SCID will have already been obtained and does not need to be repeated. - Medical history targeted at the cardiovascular, neurological, cognitive and other exclusion criteria. - Blood pressure and heart-rate reading. - ECG (12-lead with 3-5 minute rhythm strip). Exclusionary conditions documented on ECG include: Wolfe Parkinson White syndrome Myocardial ischemia and infarction Complete left bundle branch block PR interval <120 ms or >200 ms Prolonged QT interval (corrected) >500 ms Cardiac arrhythmias as defined by PACs >3 per min or PVCs >1 per min - Urine drug test, as a possible indication for substance abuse or dependence (may be repeated at any time during the study if intoxication is suspected) - Alcohol breathalyzer test, as a possible indication for alcohol abuse or dependence (may be repeated at any time during the study if intoxication is suspected) - Urine pregnancy test for females (also performed at the beginning of the cognitive training phase, and every two weeks thereafter) - Targeted questions about smoking history and motivation to stop smoking - Breath CO reading, as an indicator of smoking status and frequency - Listing of all currently taken medication - Vision test - The Addiction Severity Index - Drug and Alcohol Use subscale as an indicator for substance abuse or dependence. - The Wechsler Abbreviated Scale of Intelligence (WASI), as an indicator for possible mental retardation. Volunteers who pass the screening will be randomized to either the nicotine group or the placebo group. Randomization will be performed by the MPRC's biostatistician, [name], upon receiving a randomization request from the research assistant coordinating the study or a study investigator. Participants are then scheduled for a first NICOTINE EXPOSURE SESSION. In this session, participants will consume a nicotine lozenge (2 mg for non-smokers, 4 mg for smokers) if they have been randomized to the nicotine group and a placebo lozenge if they have been randomized to the placebo group. The number of smokers will be counterbalanced between the nicotine and placebo group. Participants will be instructed not to eat or drink within 15 min prior to or while consuming the lozenge. Participants are asked to report any adverse effects as soon as noted and to rate their subjective state immediately before the lozenge and every 30 min thereafter (see Side-Effects Checklist under "Additional Documents"). At this time, an investigator will also take their blood pressure and heart rate. The adverse effects of nicotine develop rapid tolerance. If any adverse effects are observed that are greater than "mild" and were not present pre-lozenge, the participant will undergo another lozenge exposure session on a separate day before starting the study. This may be repeated up to 4 times. Once both the participant and the investigator judge that any untoward effects of the lozenge are mild and tolerable and will not interfere with the cognitive training, the first outcome measurement session is scheduled, and the daily training sessions will commence the day after. A smoker who cannot tolerate the 4-mg lozenge may be dosed with a 2-mg lozenge in the cognitive training phase (the study would be single-blind for this subject). A participant who cannot tolerate the 2-mg lozenge even after repeated attempts will be excluded from the study. Participants who with the 2 mg lozenge display a rise in blood pressure by >20 mm Hg relative to pre-lozenge, a rise in HR to >120, or vomiting, will also be excluded from the study. OUTCOME MEASUREMENTS will be performed before the training begins, and approximately every 4 weeks after that until 4 weeks after the training ends. During the training phase, the outcome measurements will be performed AFTER completion of the daily cognitive training session. We will always schedule at least 1 hour between training and the outcome measurement, during which the participant can rest or have lunch. Outcome assessments are: a) The MATRICS Consensus Cognitive Battery (MCCB), an FDA-approved assessment tool for trials of cognition-enhancing treatments in PSZ. The battery measures 7 domains: speed of processing, attention/vigilance, working memory (verbal, nonverbal), verbal learning, reasoning, problem solving, and social cognition. b) The progression in training exercise parameters since the last outcome measurement time point (see below). c) Symptom assessments: the Brief Psychiatric Rating Scale, Scale for Assessment of Negative Symptoms, and Calgary Depression Scale. d) The state version of the State-Trait Anxiety Inventory. e) The Cogstate computerized assessment battery. Further outcome measures taken only pre- and post-training (week 0 and 10): a) Working Memory capacity (K) derived from a computerized change localization task. Two to four colored squares are shown for 100 ms. After a delay, they reappear and the task is to click on the one square that has changed color. b) The UCSD Performance-Based Skills Assessment, measuring ability to perform real-life tasks by standardized role-play. c) Quality of Life Scale, measuring functional outcome and quality of life in PSZ. d) The trait version of the State-Trait Anxiety Inventory. e) The Cognitive Assessment Interview (CAI), a brief interview-based measure of daily life cognitive functioning, administered to both the PSZ and a close relative or caretaker. The CAI was developed based on two longer scales and assesses 10 items related to working memory, attention/vigilance, learning/memory, problem solving, processing speed, and social cognition, with little or no repetition effects. f) Questionnaire asking each participant to guess their treatment group (nicotine or placebo; post-training only). g) A 5-ml venous blood sample will be taken, centrifuged, and frozen. At the completion of the study, the samples will be analyzed for TNF alpha, and potentially other inflammatory markers, to test whether repeated nicotine exposure may have anti-inflammatory effects that may be related to any effects on cognitive outcome measures. If a participant declines to have their blood drawn but are otherwise eligible for the study, they may participate without the blood draws. COGNITIVE REMEDIATION TRAINING PROCEDURE Prior to each daily training session, participants will complete a brief checklist about their caffeine and cigarette consumption today (how much/how many), when they last smoked/drank a caffeinated beverage, how many hours of sleep they got the previous night, when they last drank alcohol and how much. Prior to each session, smokers also provide a CO breathalyzer reading. Each training session will include ~30 min of auditory and ~30 min of visual training exercises by Posit Science, in a counterbalanced manner. The auditory training consists of six exercises: fast and accurate discrimination of (1) sound frequencies, (2) phonemes and (3) syllables, and recall of syllables, (4) sequences of syllables, (5) multi-element verbal instructions, and (6) details of a narrative. The visual training consists of five exercises designed to (1) improve visual precision, (2) increase capacity to divide visual attention, (3) improve visual memory, (4) expand field of view, and (5) increase visual processing speed. The programs train the fine-tuned and differentiated processing of sensory input and engage attention, working memory and/or executive processes. To induce the right level of challenge and promote engagement and motivation, task difficulty adjusts continuously to user performance to maintain ~85% correct responses (which are rewarded by auditory and visual feedback). Adjustable parameters include presentation time, interstimulus interval, physical similarity between stimuli, stimulus eccentricity, number of stimuli, and information complexity. Some exercises provide a progress summary of these parameters after each session. These values will be recorded on all training days. Other exercises provide a separate assessment tool to monitor progress. These assessments will be performed every 4 weeks with other outcome measurements. Every Monday and Thursday, a nicotine or placebo lozenge, encapsulated in gelatin, will be administered 20 minutes prior to the beginning of the training. Nicotine lozenges are mint-flavored "mini" lozenges, placebo lozenges are size-matched breath mints. Smokers in the Nicotine Group will receive a 4-mg lozenge. Plasma concentrations after this dose resemble the "nicotine boost" typically seen in dependent smokers by smoking a single cigarette (~1 ng/ml). Non-smokers in the Nicotine Group will receive a 2-mg lozenge because 4 mg in nicotine-naïve individuals would likely result in low tolerability. Participants will be instructed not to eat or drink within 15 min prior to or while consuming their lozenge. Participants may perform the training sessions at the Maryland Psychiatric Research Center (MPRC), or, in a separate room, at their day program or inpatient unit if applicable (a research associate would visit daily with laptop, lozenge or assessment instruments). The lozenge would be administered by a local nurse or other medical professional if possible, else these sessions would be performed at the MPRC. Participants who are unable to come to the MPRC or day program to complete the training (e.g., because they work or live too far away) may perform the exercises at home if they have internet access and their clinician or study staff considers them capable of doing so reliably. The CO measurement would be omitted on home-training days, and participants would be given the questionnaire about how much they slept and how much caffeine or alcohol they consumed to complete by themselves at home. On the two weekly lozenge days, they would be scheduled to perform the training at the MPRC. Under select circumstances, when the patient is unable to come to the MPRC on those days, too, they would be instructed to take the lozenge at home, following doctor's orders. A study team member would call them at home and

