If you uploaded a separate research protocol document in the 'Research Protocol' page, cite the applicable section and page numbers from that document in the answer boxes below.

- 1 * **List all questionnaires/surveys to be used in the study, including both standardized and non-standardized assessments:**
 Questionnaire asking about hours of sleep, caffeine and cigarette consumption today, to be used on each training day.
 Psychiatric and non-psychiatric medication forms, to record all currently taken medication
 Side-effects checklist to be used in the nicotine exposure session(s)
 The state- and the trait-version of the State-Trait Anxiety Inventory
 The Reasons for Smoking questionnaire
 The Nicotine Use Questionnaire
 The Nicotine Dependence Questionnaire
 A questionnaire recording the participant's guess as to whether or not their lozenges contained nicotine (Treatment Group Guess), to be completed with the outcome measurement immediately following training completion.
 A medical history pre-screening questionnaire, to be performed by a research assistant prior to the Medical History by the physician.

- 2 * **Upload a copy of all questionnaires/surveys:**

Name	Created	Modified Date
Medical history pre-screen	12/12/2013 3:22 PM	12/12/2013 3:31 PM
Treatment Group Guess	12/10/2013 4:15 PM	12/10/2013 4:15 PM
Nicotine Dependence Questionnaire	12/10/2013 4:02 PM	12/10/2013 4:02 PM
Nicotine Use Questionnaire	12/10/2013 4:01 PM	12/10/2013 4:01 PM
Reasons for Smoking Questionnaire	12/10/2013 4:01 PM	12/10/2013 4:01 PM
State-Trait Anxiety Inventory - Trait version	12/10/2013 4:00 PM	12/10/2013 4:00 PM
State-Trait Anxiety Inventory - State version	12/10/2013 4:00 PM	12/10/2013 4:00 PM
Side-Effects Checklist	12/10/2013 3:58 PM	12/10/2013 3:58 PM
Non-Psychiatric Medication Form	12/10/2013 3:57 PM	12/10/2013 3:57 PM
Psychiatric Medication Form	12/10/2013 3:56 PM	12/10/2013 3:56 PM
Sleep-Smoke-Caffeine Questionnaire	12/10/2013 3:44 PM	12/10/2013 3:44 PM

3 * What is the total length of time that each survey is expected to take?

Sleep-Smoke-Caffeine Questionnaire: 3 min

Medication forms: 10 min

Side Effects Checklist: 5 min

STAI - State: 4 min

STAI - Trait: 4 min

Reasons for Smoking Questionnaire: 3 min

Nicotine Use Questionnaire: 5 min

Nicotine Dependence Questionnaire: 5 min

Treatment Group Guess: 2 min

Medical history pre-screen: 5 min

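### None of the 20 training lozenges has a scheduled post-dose side-effect check; one neutral end-of-session question would close a modest gap cheaply

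*Combined protocol and SAP*

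**What the plan says.** All places are in the combined protocol and SAP.

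**Exposure session(s), before training.** Under Study Procedures, item 1, participants "rate their subjective state immediately before the lozenge and every 30 min thereafter", with blood pressure and heart rate taken at the same times. Research Related Risks, item 1, sets this monitoring at 3 hours. If effects are worse than mild, another session follows on a separate day: "This may be repeated up to 4 times". Surveys/Questionnaires, item 1, assigns the form to this stage only: "Side-effects checklist to be used in the nicotine exposure session(s".

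**Training lozenge days.** Study Procedures, item 1, schedules a form before the session: "Prior to each daily training session, participants will complete a brief checklist about their caffeine and cigarette consumption today". It also covers sleep and alcohol, and smokers give a breath carbon monoxide reading. No post-lozenge question or reading is scheduled.

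**Outcome days.** Symptom and anxiety scales are given during training, but on days without a lozenge: "OCMs are assessed on a non-drug day (Wed", in Justification, Objective, & Research Design, item 2.

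**Cover during training.** A research assistant is usually present (Behavioral Intervention, item 1). Investigators can be reached if training causes distress, and emergency services would be called for a severe lozenge reaction (Resources, item 3). At community sites, "The lozenge would be administered by a local nurse or other medical professional if possible, else these sessions would be performed at the MPRC". Anyone who leaves because of nicotine effects is asked to stay for monitoring until a physician is satisfied (Withdrawal of Participants, item 3). Home trainees are scheduled at the research center on lozenge days. In select circumstances they may take the lozenge at home after a reminder call.

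**The concern.** Most of the nicotine in this trial is given during training, and the plan does not schedule a question about side effects after any of those doses. The listed effects include dizziness, palpitations, nausea and chest pain, which an assistant supervising computer exercises may not see. If the participant does not volunteer them, they go unrecorded. The safety board's review of adverse events would then combine solicited information from the exposure doses with unsolicited information from repeated dosing.

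The exposure session cannot fully stand in for later doses. Research Related Risks accepts that cigarette and lozenge nicotine may overlap in smokers, and smoking before a session can differ from day to day. Participants may also enter training with effects judged mild and tolerable, and nothing scheduled follows these up. At stake is the completeness of the safety record and the early notice of a problem in an individual. The efficacy hypotheses do not depend on tolerability.

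**Working it through.** **Number of training lozenges.** Two per week (Monday and Thursday) for 10 weeks: 2 × 10 = 20. This reproduces the 20 lozenge sessions that the plan uses under Hypothesis 2a (Sample Size and Data Analysis, item 1).

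**What is scheduled after a dose.**

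| Occasion | Lozenge given | Side-effect rating after dose | Blood pressure and heart rate after dose |
|---|---|---|---|
| Screening | No | Not applicable | Not applicable (one reading, no dose) |
| Each exposure session | Yes | 180 min / 30 min = 6 | 6 |
| Training lozenge day, on site | Yes | 0 | 0 |
| Training lozenge taken at home | Yes | 0 (call comes before the dose) | 0 |
| Outcome day | No | Not applicable | Not applicable |

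**Share of doses without a scheduled check, fully adherent participant.** Exposure lozenges number 1 at least and 1 + 4 = 5 at most, reading the repeat rule as up to four further sessions.

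- One exposure lozenge: 20 / (20 + 1) = 95%.
- Five exposure lozenges: 20 / (20 + 5) = 80%.

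**Nicotine arm, 25 entrants, all doses taken.** 25 × 20 = 500 training doses. The total is 500 + 25 = 525 to 500 + 125 = 625, so the share is again 95% to 80%. The 80% end requires every entrant to need all four repeats. Participants who stop early have a lower share.

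**Time since the last scheduled check.** Study Procedures, item 3, allows up to 3 months (about 13 weeks) between the last exposure session and training. The last check therefore falls about 0 + 10 = 10 weeks to 13 + 10 = 23 weeks before the last lozenge, if no training week is postponed.

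**Timing of an end-of-session question.** The lozenge precedes training by 20 min. Exercises take about 30 + 30 = 60 min in Study Procedures; Behavioral Intervention gives an 80-min session. The question would fall at 20 + 60 = 80 to 20 + 80 = 100 min after the dose, past the plasma peak that Research Related Risks puts at about 1 hour.

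**The case against.** The strongest defense is that monitoring was deliberately concentrated on the first doses. The plan says that adverse effects show rapid tolerance. Training starts only when participant and investigator judge any effects mild and tolerable. Dosing is twice a week, and 4 mg in smokers is likened to the boost from one cigarette. The lozenge is an approved product given after medical screening. Intensive checks first and reactive cover later is a defensible design, and it keeps the expected risk modest. The reactive cover is also real: staff are usually present, help can be reached, and community lozenges depend on sites with "If the local site has nursing or other medical staff who are willing to administer a lozenge that may contain nicotine". All of this stands, and it limits the weight of the point. It does not supply a scheduled question.

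The percentages count doses. They do not estimate missed events, and the documents give no figure from which to do so.

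Stronger readings are tempting, but the documents do not support them:

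- A reader might infer that participants are unsupervised in training. The provisions above contradict that.
- From "Participants who with the 2 mg lozenge display a rise in blood pressure by >20 mm Hg relative to pre-lozenge" a reader might infer that smokers on 4 mg lack a stopping rule. The same text lets a smoker who cannot tolerate 4 mg step down to 2 mg, which explains why exclusion is tied to 2 mg. Research Related Risks repeats the thresholds without a dose, and Withdrawal of Participants allows removal for unsafe nicotine effects.
- A reader might want the exposure-session blood pressure used as a reference in training. By the last lozenge it could be about 23 weeks old, and ordinary variation could then exclude participants wrongly.
- A reader might ask for reporting to the safety board by arm. The Internal DSMB plan presents data in aggregate and invites the principal investigator to meetings, so that would put blinding at risk.

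The Study Manual, the Doctor's Orders and the consent form are not available here. Any of them could contain instructions on reporting side effects.

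**Conclusion.** The point holds as a minor safety improvement. In the protocol text, post-dose side-effect ratings, blood pressure and heart rate are scheduled only at the pre-training exposure session(s), and 0 of 20 training lozenges has a scheduled post-dose side-effect check. That is 80% to 95% of a participant's lozenges, assuming full adherence and one to five exposure sessions. Cover is thinnest for the occasional home lozenge. The conclusion does not say that the trial is unsafe or that its stopping rules need rewriting. It says that side-effect data during repeated dosing depend on who speaks up, in a study that the plan itself rates as greater than minimal risk, and that this can be changed at little cost.

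**What to change.** By protocol amendment:

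- At the end of each lozenge-day session, ask every participant in both arms one neutral question about side effects since the lozenge, in identical words.
- After any lozenge taken at home, make a short follow-up call with the same question.
- Record the answers as adverse-event data for the board's existing aggregate review.
- Keep the answers from outcome raters where possible. Research assistants run the training and may also rate outcomes (Resources, item 3; Interviews, item 4), so separate recording matters.

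The cost is a few minutes per lozenge day. Even if the question took as long as the full Side-Effects Checklist (5 min in Surveys/Questionnaires, item 3), the total would be 5 × 20 = 100 min per participant over 10 weeks. To this add one call per home lozenge. The downside is that repeated questions may prompt guesses about allocation, by participants or staff. Identical neutral wording limits this but does not remove it. The existing Treatment Group Guess questionnaire would show guessing by participants after training, but not by raters.
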